5.2 EXCLUSION CRITERIA

5.2.1. Patient Exclusion Criteria The few individuals for whom there is a need for precaution in using NRT will be excluded

- recent myocardial infarction (2 weeks)
- serious underlying arrhythmias
- patients who are pregnant or nursing
- any patient who participated in the study during wave 1 at OPC site 1-5 and then transferred to OPC site 6-13 during wave 2

We will also exclude those who are unable to demonstrate capacity for consent and patients already enrolled in a tobacco use treatment program.

Our pilot data indicate that about half of tobacco users in these sites are dual users (cigarettes and waterpipe); only about 12% use waterpipe alone. VQUIT found that dual users who received VHW counseling had 6-month CO confirmed quit rates that were comparable to patients who used cigarettes only. Therefore, we will not exclude dual users. We will exclude waterpipe only users because the intervention is based on effectiveness data for dual and cigarette users and there is a lack of evidence for efficacy or effectiveness of NRT use in this population.

5.2.2. Employee exclusion criteria. Employees who are unwilling to sign consent will be excluded.

5.3 VULNERABLE SUBJECTS. Employees are considered a vulnerable population. Research staff who work for the research institute (ISMS) will be responsible for consenting employees. Research staff are trained to emphasize that participation is voluntary and employees' decision will not affect their job evaluation, promotions and work-related assignments.

5.4 STRATEGIES FOR RECRUITMENT.

5.4.1. AIM 1. We will work with the Hanoi CDC who will contact OPCs to inform potential study sites for about the study aims and obtain permission to have ISMS research staff contact them to provide additional information and assess eligibility. We will then reach out to set up a meeting with the medical directors to describe the study. If they are interested in participating the site will be enrolled. For individual interviews, patients will be screened at one of the three OPCs that agree to participate in the Aim 1 data collection. They will be screened for current tobacco use in the waiting room, asked to participate if they meet eligibility criteria, and given a date and time for the interviews. Verbal consent will be obtained prior to completing the screening questionnaire. Health care providers who work in the participating OPCs will be asked to attend a brief meeting in that site. Providers will be told about the project, including the data collection. They will be asked if they are willing to participate in the KIs at baseline (AIM 1). Those who agree will be contacted by a Research Assistants (RA) to set up a time for KI and obtain verbal consent. The pilot study will use the Aim 2 RCT recruitment approach. (see below)

5.4.2. AIM 2. 13 OPCs will be enrolled in the study as per the protocol described above. We propose to enroll 672 patients (48 per site). Patients arriving for previously scheduled clinic visits will be asked about their tobacco use by a trained nurse who is responsible for checking patients in at the time of their visits. The nurse will describe the study and screen for eligibility. Eligible patients will be introduced to the RA who will be onsite. The RA will read the consent and if the patient is willing to participate and signs the consent form the RA will enroll them, complete the baseline survey and randomize to one of the three study arms. Health care providers will again be asked to participate in a brief meeting to discuss the details of the RCT. We will then use the same recruitment process as in AIM 1. However, at this time we will be obtaining written consent to complete baseline and 12-month surveys and a post intervention KI at 12 months.

5.4.3. AIM 3. At the time of enrollment in AIM 2, providers will also be asked to participate in the KIs 12 months after the intervention period. Consent will be obtained at the time they enroll in AIM 2. For the 18-month sustainability survey, written consent will be obtained at the time they are approached to participate in the survey.

5.4.4. Aim 4. We will enroll 75 patients who are non-smokers using the same strategy as AIM 2.

5.5 DURATION OF STUDY PARTICIPATION. Patient individual interview participants will be asked to participate for the single session. Providers and patients who participate in the RCT will be enrolled for 2 years. Patients who are non-smokers (n=75) participating in the diversity supplement study will be enrolled for six months.

5.6 TOTAL NUMBER OF PARTICIPANTS AND SITES. For Aim 1, we will conduct 24 patient interviews and 28 provider interviews across 3 OPCs. We will recruit 16 patients in the one OPC that will serve as the pilot study site. For Aim 2 we include 672 patients (48 patients per site, 16 per arm). Surveys will be conducted, at baseline, with all health care providers in the 13 sites in person (n=98). For Aim 3, we will repeat surveys and KIs among the 48 providers with 2 health care providers per site, 13 sites, (n=28) at 12-months post intervention, and will separately conduct a sustainability survey at 18-months with the same providers. For Aim 4, we will include 75 patients (at least 5 patients per site).

5.7 PARTICIPANT WITHDRAWALS OR TERMINATION.

5.7.1. Reason for withdrawal. This is a minimal risk study so we do not expect participants to withdraw for a safety-related issue. However, participants (providers and patients) are free to

withdraw from participation in the study at any time upon request without any impact on their ability to continue to receive care or to be employed.

5.7.2. Handling of withdrawal. We will track all withdrawals and reasons for withdrawals. Participation is voluntary and all study participants may withdraw from the study at any time without penalization. However, patient participants in the Aim 2 RCT will be encouraged to continue to participate in the primary outcome assessment of smoking cessation (i.e., follow up telephone surveys and if reported quitting, return for subsequent carbon monoxide assessment), unless a participant withdraws consent. Patients and providers enrolled in the longitudinal monitoring of cessation (patient surveys) and provider-level constructs (provider surveys and KIs) are considered lost to follow up after 4 attempts to contact them by phone. No replacement of participants who withdraw or discontinue early will occur. Date and reason for withdrawal will be recorded.

5.8 PREMATURE TERMINATION OR SUSPENSION OF STUDY. This study may be temporarily suspended or prematurely terminated if the Ministry of Health retract their current strong support for this project. Written notification, documenting the reason for study suspension or termination, will be provided by the suspending or terminating party to the study principal investigators (PI) ([name]). If the study is prematurely terminated or suspended, the PIs will promptly inform the IRB and will provide the reason(s) for the termination or suspension. Circumstances that may warrant termination or suspension include, but are not limited to: a) Insufficient compliance to protocol requirements, b) Loss of institutional political support, c) Determination that the study procedures are too invasive. The study may resume once concerns about safety, protocol compliance, data quality are addressed and satisfy the sponsor and/or IRB.

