AIM 4: We will collect data on food insecurity from 75 non-smokers and 672 smokers at baseline and 6-months.

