4.2 STUDY ENDPOINTS
4.2.1 Primary. The primary endpoint is carbon monoxide confirmed smoking abstinence at 6 months.

4.2.2 Secondary. The secondary patient outcomes are self reported smoking cessation and reduction in number of cigarettes per day, and hypothesized mediators of the main outcome (risk perception, attitudes, norms and self-efficacy) at 3 and 6 months.

5. STUDY ENROLLMENT AND WITHDRAWAL.

5.1 INCLUSION CRITERIA.

5.1.2. Study site eligibility. We will recruit 13 OPCs from one city, Hanoi. The sites are very homogeneous in terms of staffing and infrastructure. Therefore, site eligibility will be based solely on the number of active patients to ensure adequate recruitment (>240 patients) and at least 4 providers per site. The CDC of Hanoi will assist with site recruitment.

5.1.3. Patient inclusion criteria. For Aim 1-3 men and women who are ≥ 18 , patients in the HIV OPCs, current tobacco users, live in Hanoi and reachable by phone are eligible. All patients of the OPCs are HIV+. We expect fewer women to be enrolled in all phases of this research because about 10-20% of patients in the OPCs are female, and their smoking prevalence is low (<2%). There are no enrollment restrictions based upon race and ethnicity. For the supplement we will enroll men and women who are >18 and patients in the HIV OPCs who are not current tobacco users.

5.1.4. Health care providers and staff inclusion criteria. All providers and staff currently working at the OPC will be eligible.

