AIM 4: When comparing smokers and non-smokers at baseline on the HFIAS, power is 80% to detect a standardized mean difference of $d=0.46$ (about half a standard deviation, a difference of 3 HFIAS points assuming a standard deviation of 6) given the proposed sample size of $n= 150$ (75 smokers and 75 non-smokers). When estimating the relation between income and HFIAS, power is 80% to detect a squared multiple correlation of $R^2=.05$ given the proposed sample size of $n=150$. When estimating the impact of smoking cessation on HFIAS at the 6-month follow-up, power is 80% to detect a standardized mean difference of $d=0.89$ (about nine tenths of a standard deviation, a difference of 6 HFIAS points) given the proposed sample size of $n=75$ smokers at baseline and assuming at least 16% of smokers ($n=12$) achieve cessation.

9.2 STATISTICAL HYPOTHESIS. The primary hypothesis is that more intensive counseling delivered by a trained nurse (ARM 2) will be more effective than provider brief counseling plus Quitline counseling (ARM 1) in increasing smoking abstinence. We further hypothesize that adding nicotine replacement therapy to the more intensive counseling will increase cessation rates more than the intensive counseling alone (ARM 3).

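### Aim 4 recruits non-smokers without regard to sex although nearly all smokers will be men, and no adjustment for sex is clearly stated for its food-insecurity comparison

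*Combined protocol and SAP*

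**What the plan says.** All references are to the combined protocol and SAP.

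- Section 5.4.4 (Aim 4 recruitment): "We will enroll 75 patients who are non-smokers using the same strategy as AIM 2". The Aim 2 strategy (section 5.4.2) is screening by a nurse as patients check in for scheduled visits. The only distribution rule for non-smokers is a minimum number per site (section 5.6).
- Section 5.1.3 (patient inclusion): "about 10-20% of patients in the OPCs are female, and their smoking prevalence is low (<2"; the last figure is 2%. The same section states "For the supplement we will enroll men and women who are >18", with no restriction or balance by sex.
- Section 3 makes the baseline difference in household food insecurity between smokers and non-smokers the first objective of the supplement.
- Section 9.1, Aim 4, opens with "When comparing smokers and non-smokers at baseline on the HFIAS" and gives 80% power at d = 0.46, glossed as "a difference of 3 HFIAS points assuming a standard deviation of 6", for "75 smokers and 75 non-smokers". It names no covariates.
- Section 9.1, Aim 2, lists sex among the patient characteristics to enter every analysis. The sentence stands under Aim 2, and the outcomes listed in that paragraph do not include food insecurity.
- The Protocol Summary adds the food-insecurity outcomes to the fixed-effects regressions stratified by clinic, but names no covariates.
- The number of smokers differs. Section 4.1, Aim 4, says "We will collect data on food insecurity from 75 non-smokers and 672 smokers at baseline and 6-months", whereas the design schematic and section 9.1 use 75.

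**The concern.** Taking non-smokers as they come at check-in gives a group with the sex mix of the clinics' non-smokers. That group contains a larger share of women than the clinics as a whole, because male smokers have been removed from it. The smoker group will be almost entirely male. If food-insecurity scores differ between men and women, part of that difference appears in an unadjusted smoker v non-smoker contrast.

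The error could go either way. If women score higher, the non-smoker mean rises and a true excess in smokers is masked. If women score lower, an excess is created or exaggerated. If the analysis does adjust for sex, the women among the non-smokers contribute almost nothing to the smoking contrast, and the stated power is too high.

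**Working it through.** **Inputs from the documents.** 75 v 75; d = 0.46; SD 6; female share of clinic patients f = 0.10 to 0.20; smoking prevalence in women under 2% (0.02 used).

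**Assumptions.** Two-sided alpha is 0.05, since none is stated for Aim 4. Male smoking prevalence p is not given, so 30-60% is used, with 70% as an extreme. Recruited patients are taken as representative of the clinics' smokers and non-smokers. As a check on the lower end, section 5.1.2 admits sites with more than 240 patients and the plan wants 48 smokers per site. A site near that floor needs 48/240 = 20% of patients to be enrolled smokers, so men must smoke at about (0.20 - 0.02f)/(1 - f) = 22-25% even if every smoker joins.

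**1. The plan's own figure.** Noncentrality = 0.46/√(2/75) = 2.817. Normal power = Φ(2.817 - 1.960) = 80.4%; the t-test gives 79.9%. The stated 80% reproduces. In points, 0.46 × 6 = 2.76, which the plan rounds to 3.

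**2. Expected sex mix.**
Female share of non-smokers = 0.98f / [0.98f + (1 - f)(1 - p)].
Female share of smokers = 0.02f / [0.02f + (1 - f)p].
Example with f = 0.20, p = 0.60: 0.196/(0.196 + 0.320) = 38.0%, and 0.004/(0.004 + 0.480) = 0.8%.

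| f | p | Women among 75 non-smokers | Women among 75 smokers | Gap (points) | Men-only power, d = 0.46 |
|---|---|---|---|---|---|
| 10% | 30% | 13.5% (10.1) | 0.7% (0.6) | 12.7 | 76.7% |
| 10% | 60% | 21.4% (16.0) | 0.4% (0.3) | 21.0 | 74.6% |
| 20% | 30% | 25.9% (19.4) | 1.6% (1.2) | 24.3 | 72.9% |
| 20% | 60% | 38.0% (28.5) | 0.8% (0.6) | 37.2 | 68.5% |

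At p = 70% and f = 20%, women are 45% of non-smokers and men-only power is 65%.

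**3. Bias if sex is ignored.** Size of bias = gap × sex difference in HFIAS. Each point of sex difference therefore gives 0.13 to 0.37 points of bias. The sex difference is not in the documents. If it were 2 to 4 points, the bias would run from 0.127 × 2 = 0.3 to 0.372 × 4 = 1.5 points, that is 9% to 54% of the 2.76 points detectable.

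**4. Error rate and power with and without adjustment.** A simulation (6,000 runs, 75 v 75, linear model, assumed 3-point sex effect with women higher) gave:

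- No true smoking effect: the unadjusted test rejects in 7% of runs with 15% of non-smokers female and in 20% with 38% female. The sex-adjusted test rejects in 5% in both cases.
- True d = 0.46: the unadjusted estimate shrinks to 0.39 and 0.27. The sex-adjusted estimate stays at 0.46, with power 77% and 69%.

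**5. If all 672 smokers are used.** The bias is unchanged. The standard error falls from 6√(1/75 + 1/75) = 0.98 to 6√(1/75 + 1/672) = 0.73 points, so an unadjusted test would reject falsely more often. Men-only power is 86-94% at p = 30-60%, and 82% at the 70% extreme.

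**The case against.** Three objections deserve weight.

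First, the plan may already adjust. The Aim 2 text calls for sex as a covariate throughout, and the Protocol Summary puts food insecurity in the same regression framework. Section 9.1, Aim 4, is a power statement, not an analysis model. This is a fair reading, but it depends on carrying a sentence from one aim to another. Two analysts could differ, and stratifying by clinic does not balance sex. Even on this reading, the 80% power ignores the cost of adjusting.

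Second, the size of the bias is not known. The documents give neither male smoking prevalence nor any sex difference in HFIAS. The scale measures household food insecurity, so a large difference by sex of respondent is not self-evident. The 1.5-point figure combines the highest female share, 60% male smoking and a 4-point sex gap that exceeds the plan's own target difference. This stands: the imbalance follows from the recruitment rule once men smoke far more than women, but the bias is conditional.

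Third, matching changes the population described, since section 5.1.3 admits both sexes. That is true of the non-smokers only; the smoker group is already almost all male.

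A reader might go further and infer that, with 0 to 1 women among 75 smokers, sex cannot be adjusted for. The documents do not support that. Across p = 30-60%, about 46 to 65 of the 75 non-smokers and nearly all the smokers would be men. A men-only analysis, or a sex covariate without an interaction, therefore identifies the contrast in men, and the simulation confirms this. What cannot be estimated is the contrast in women or a sex-by-smoking interaction.

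**Conclusion.** The point holds as a gap in design and specification. The recruitment rule produces a sex imbalance of about 13-37 percentage points at an assumed 30-60% male smoking prevalence, and the plan does not clearly say that Aim 4 adjusts for it. If unadjusted, the first supplement objective is open to confounding by sex, of unknown direction and of a size that depends on an HFIAS sex difference the documents do not give. If adjusted, the estimate is in effect for men, and power at d = 0.46 with 75 per group is about 69-77%, not 80%. The rule costs something on either reading. It affects the first objective of an observational supplement, not the randomised comparison or its primary endpoint.

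**What to change.** - In section 5.4.4, frequency-match the 75 non-smokers to the smokers on sex, which in practice means recruiting mostly men. This keeps power near the stated 80%. Supply should not be a problem: about 75/13 = 6 non-smokers are needed per site, and a 240-patient clinic with 20% women and 60% male smoking would have 240 × 0.80 × 0.40 = 77 non-smoking men.
- If recruitment is finished, pre-specify a sex-adjusted or men-only comparison as the primary Aim 4 contrast and restate its power in section 9.1.
- In either case, name the Aim 4 model and covariates under Aim 4, limit the conclusion to men, and reconcile the 75 and 672 smokers.

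The cost is a recruitment instruction or an analysis restriction. The downside is that nothing can be said about women, which the near-absence of female smokers already rules out. If the change is made only at analysis, 75 v 75 loses about 3 to 11 points of power at p = 30-60%; using all 672 smokers would more than recover that.

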6. STUDY DRUG

6.1 STUDY DRUG DESCRIPTION. Nicotine gum has been FDA approved for over 20 years. They are available as over the counter medications. Nicotine gum is a form of nicotine replacement therapy that delivers a specific dose of nicotine to people who use tobacco in order to reduce withdrawal symptoms when they are trying to quit. Gum is placed in the mouth and chewed multiple times per day.

6.1.1. Acquisition: Nicotine gum will be purchased in Vietnam.

6.1.2. Packaging and labelling. The gum comes in boxes of 12 tablets, each tablet contains 2 mg of nicotine. One box can be used for 1 to 1.5 days.

6.1.3 Storage. NRT is stored in locked cabinets at ISMS and at the pharmacy of each OPC. The medication does not require any special temperature or storage conditions.

6.1.4 Dosing, route of administration and duration of therapy. All patients will receive 6 weeks of 2 mg nicotine gum.

6.1.5 Dose adjustments. All patients will be given a one-page information sheet that explains potential side effects and includes the site study PI contact information. If a patient who is experiencing side effects associated with a need to reduce the dose (i.e., palpitations, nausea, light headedness) we will change the number of pieces of gum used per day. This is extremely rare and usually due to the fact that the patient is continuing to smoke while using the gum. Patients will be advised, again, to not smoke while using NRT.

6.1.6. Tracking dose. The counselors have a tracking form to assess use of NRT. This form is completed at each counseling session and includes three questions that ask if the patient used the NRT provided, if the patient used the gum since the last session as directed, how many pieces of nicotine gum they used since their last session and how many boxes were used.

6.2 STUDY AGENT ACCOUNTABILITY PROCEDURES. ISMS research staff will be responsible for dispensing the NRT to OPC pharmacies. Subjects will receive 6 weeks of gum starting at the first week of counseling and dispensed at each follow up session up to 6 weeks. We will order enough for the number of subjects we plan to enroll in ARM 3 which includes NRT. RAs will sign out the number of boxes they are taking to the field during the enrollment period and give NRT to the

pharmacist. When providing the gum to patients, the pharmacists will input patient name, date, time, the patient's ID, # boxes provided, the lot number for each box and expiration date on the NRT tracking form. The patient will sign that form to indicate that they have received the medication to the patient. All NRT not dispensed (because of fewer enrollees on a particular day) will be returned to the ISMS office and locked in a storage cabinet. Regular study drug reconciliation will be performed to document drug assigned, drug consumed, and drug remaining. See Section 6.3.6 for how counselors will track patient NRT use. . Reconciliation will be logged on the drug reconciliation form, and signed and dated by the study team. At the end of the study period we will destroy all unused medication as per safety instructions for discarding NRT gum.

6.3. STUDY INTERVENTION ARMS

6.3.1. *Randomization*

Once RAs enroll a patient in the study and the baseline survey is completed (i.e., signed consent), they will use a preprogrammed system in REDCap to randomize patients to one of the three study arms. Our biostatistician will create the REDCap database that will prompt randomization to the appropriate condition.

6.3.2. *Administration of Intervention.* Below we describe the protocol for the RCT intervention components. The materials related to the intervention described below (i.e., brochures, counseling manual and counseling session tracking booklet) will only be used after NYULH and local site IRB approval are obtained for these documents.

ARM 1. Ask, Advise, Assist (AAA) and Refer. The research team will send patient contact information to the Quitline which will proactively call the patient. We will train providers and develop a tool kit that will include information for providers and patients.

ARM 2: AAA plus referral to onsite counselor (Counsel). Multisession counseling: We will

Table 2. Counseling protocol		
Sess.	Wk	Content
1	1	Build motivation, significance of quitting for HIV+ smokers, elicit triggers, quit plan
2	2	Dealing with withdrawal, managing stress, refusal skills
3	3	Managing high risk situations (e.g., other substances), coping with thoughts and feelings
4	4	Review problem solving, stress management and building social support
5	8	Maintaining commitment and motivation, anticipating and preventing slips
6	12	Successes and challenges, long term relapse prevention

provide a packet for each patient randomized to ARM 2 or 3 to the designated nursing staff that has been trained to provide the counseling intervention that includes all intervention handouts. The nurse counselor will receive a manual, session tracking booklet and fidelity checklist. Nurse manuals will include additional information about NRT to be reviewed with patients in ARM 3 and a document to use to track the use of the nicotine

gum during each session. Our decision to train nurses is consistent with the staffing infrastructure, recommendations from the OPC directors and Provincial health directors and [name] experience working in these sites. Participants will receive six sessions of in person and telephone counseling depending on their preferences (**Table 2**). There is evidence that a greater number of sessions may be associated with higher smoking abstinence rates among PLWH, but these outcomes are short-term (3 month), with a loss of effect by 6 months. Therefore, there is no definitive research on the optimal number of sessions that will lead to long-term outcomes in PLWH. Rather, the literature suggests that it is not only the number of contacts but also the timing (i.e., need for contact over a longer period of time to maintain abstinence).⁴⁻⁸ Therefore, the number of sessions and timing is based on an extensive review timing (i.e., need for contact over a longer period of time to maintain abstinence).⁴⁻⁸ Therefore, the number of sessions and timing is based on an extensive review of the literature, including relevant research conducted by [name] (consultant) among PLWH in Viet Nam⁹⁸ and our pilot research that explored feasibility based on patient and counselor time demands.

Patients will receive 4 sessions in the first 4 weeks and sessions at 8 and 12 weeks that focus on maintaining long-term abstinence (**Table 2**). The first session will last 45 minutes and the following sessions about 30 minutes each. The first session will be scheduled within one week, with sessions 2 through 4 scheduled weekly and the two additional sessions scheduled for weeks 8 and 12. The counseling manual, tailored to PLWH in Viet Nam, will integrate motivational interviewing techniques with a social cognitive skills building approach, both of which have been found effective in increasing long-term abstinence in general populations of smokers and short-term abstinence in PLWH and in smokers enrolled in the VQUIT counseling intervention.⁴⁻¹⁵

ARM 3: AAA+Counsel+N (Nicotine gum). At the end of the first session patients will be taken to the pharmacists who will give participants the first week supply of nicotine gum and a one-page instruction sheet on use, potential side effects and who to call if they have concerns. ARM 2 and 3 will receive two text messages daily for 8 weeks and then 1 per day for 4 weeks to reinforce the counseling protocol.

6.3.3. Procedures for Training Interventionalists and Monitoring Intervention Fidelity.

6.3.4. Clinician Training: All clinical and support staff will attend a 2-day training that includes building skills to screen all patients for tobacco use, offer brief cessation advice and refer patients to the Quitline. We will conduct a one-day booster training after 3 months to reinforce treatment protocols and concepts. *In VQUIT, we achieved 98% attendance for the 3-day training.* The curriculum for this proposed study is being adapted from the VQUIT training which was informed by the US Guideline: *Treating Tobacco Use and Dependence*,¹⁰ additional literature on effective interventions for TUT⁸⁻¹⁰ and the World Health Organization's (WHO) guideline: "Strengthening Health Systems for Treating Tobacco Use".¹⁶ Based on findings from AIM 1, we will further adapt the training to address HIV-specific consequences of tobacco use and barriers to quitting. The training will be conducted by Drs. [name] and [name]. We will evaluate the adequacy of training with *pre-and post-surveys at the initial and booster trainings*. ISMS staff and [name] will make the training available online to address potential staff turnover (which is rare in these sites) and to increase potential for dissemination in HIV OPCs.

6.3.5. Counselor Training. Two nurses from each site will participate in a 4-day training with the that will include an interactive approach using videotaped examples of counseling techniques and role-playing to ensure proficiency in motivational and skill building techniques. The counselor training is based on the curricula that was adapted for VQUIT and will be further tailored for this study (AIM 1). Counselors will receive monthly supervision by trained ISMS staff and attend a booster training one month after the initial training. Standardized training, supervision and the inclusion of a booster session will help ensure intervention fidelity.

6.3.6. Fidelity. We will assess fidelity in several ways. Patient baseline and 3- and 6-months surveys will assess receipt of standard care (i.e., brief provider advise if they spoke with the Quitline). We will assess NRT use at each counseling session up to week 6). Counselors will ask patients: How many boxes of NRT did you use since the last session, if the patient used the gum since the last session as directed, and how many pieces of NRT are you chewing each day?

Fidelity to counseling manual: After each contact, counselors will also complete a fidelity checklist which is used as our primary measure. ISMS staff will review observations and checklists in supervision meetings. Additionally counseling sessions will be assessed by asking the counselors to record a random sample of sessions. A trained RA will listen to tapes and use a checklist to assess adherence to the manual.

Fidelity to treatment condition assignment: To reduce potential for contamination our REDCap database will prompt randomization to the appropriate condition and pharmacists will provide the NRT to participants to ensure only those in ARM 3 receive the medication. Given the additional training and time required to deliver counseling, we do not expect that participants assigned to ARM 1 will receive the intensive counseling we are testing in ARM 2 and 3. This was confirmed in

the pilot study. However, 3- and 6-months follow-up patient surveys will assess any use of NRT and other cessation services across all study arms.

6.3.7 Assessment of Subject Compliance with Study Intervention. As noted above, counselors will track completion of all sessions and we will track use of NRT will be tracked by both the counselors.

